4.2. Scientific Rationale for Study Design

As a component of the clinical development of zavegeptan, future pediatric studies will be conducted to evaluate the safety, tolerability, and PK of zavegeptan in participants 6 to less than 12 years of age with migraine. Recruiting and retaining pediatric patients in clinical trials has always been challenging due to a variety of factors, including inconvenience with patient preferences. To overcome some of those challenges, it is essential to prioritize patient-centric approaches that cater to the unique needs of pediatric patients. One such approach is PCS, which aims to reduce the burden on pediatric patients by minimizing the volume of the biological samples required and being less invasive with minimal pain compared to the venous phlebotomy collection method, which is particularly beneficial for pediatrics who are fearful of needles. Additionally, PCS offers greater flexibility to pediatric patients and their families by allowing at-home sample collection for those who may have difficulty traveling to clinics.

To allow the use of PCS in zavegeptant pediatric studies, a bridging or comparative study comparing the PCS approach with an equivalent conventional sampling technique is needed as a regulatory expectation to demonstrate the concordance of data from PCS in a controlled environment prior to implementation in large-scale clinical trials.³⁶ Therefore, the primary objective of this study is to establish the correlation between zavegeptant concentration from samples collected using PCS devices compared to conventional venous blood sampling. PK sampling time points and duration, as described in [SoA, Table 2](#), were selected to adequately capture the rapid absorption of zavegeptant, since it has a T_{max} of 0.54 hours, as well as zavegeptant elimination phase. Based on zavegeptant PK data, zavegeptant has an elimination half-life of ~ 3 hours and an effective half-life of 6.55 hours following a single zavegeptant 10 mg IN dose. For Tasso bridging analysis, having PK samples that covers zavegeptant relevant concentration up to 12 hours will be sufficient to have adequate concentration-time comparison between the 2 methods. While for the Japanese participants, having PK timepoints up to 24 hours will cover >3 half-lives, which will be sufficient to adequately estimate zavegeptant half-life in Japanese. That's why 24 hours PK samples will only be requested for Japanese enrolled participants, as described in [SoA, Table 2](#).

A healthy participant population is considered for the study because healthy participants with no concomitant diseases and using no concomitant medications represent a homogenous population allowing for proper evaluation of the PK, safety, and tolerability of a drug without confounding factors. Six PK samples will be collected from the Tasso devices at the same time of collecting venous blood samples, as described in the [SoA, Table 2](#). Those 6 Tasso-venous paired samples collected in 7 participants for each device ($7 \times 6 = 42$ data points) are sufficient to meet the scientific community recommendation for having an adequate Tasso-venous phlebotomy PK bridging study.³⁶ Different PK sampling times were selected to cover the concentration-time profile of zavegeptant IN. Of note, blood-to-plasma ratio samples will be aliquoted from the same venous blood draw as specified in the [SoA, Table 2](#). These samples will be crucial for determining the blood-to-plasma ratio value for each participant to convert the dried blood concentrations collected using Tasso-M20 to their equivalent plasma concentrations for adequate comparison between the 2 methods.

If feasible, 4 Japanese participants will be enrolled among the 14 participants planned for this study to determine the PK and safety of zavegeptant IN in this population since there is no PK and safety data available for the use of zavegeptant IN in this population. Leveraging this data will be useful in supporting the development of zavegeptant IN in Japan. However, the recruitment of these Japanese participants will be optional, and the completion of this trial will not require their enrollment.

As noted earlier, data from clinical trials of zavegeptant IN formulation have shown dysgeusia (bad/metallic/bitter taste) as the most common treatment-emergent adverse event following zavegeptant administration (refer to IB). We hypothesize that the mechanism of dysgeusia associated with zavegeptant nasal spray administration relates to the postnasal dripping of residual spray into the oral cavity and contact with the posterior tongue and taste buds, triggering the taste receptor cells. To test this hypothesis and better understand this adverse event (its intensity, onset, and duration), a taste assessment questionnaire will be performed at 1 (immediately after dosing), 5, 10 and 20 minutes after zavegeptant IN administration.

Previous case studies have shown that simple interventions like sucking butterscotch or drinking a fruit punch–flavored powdered drink have successfully managed dysgeusia following the use of sumatriptan or esketamine nasal sprays, respectively.^{37,38} Therefore, finding strategies to mask zavegeptan-induced bitter taste can help improve patient experience and adherence. As an exploratory objective, this study will explore whether giving a butterscotch candy before zavegeptan IN administration will help manage dysgeusia. To do that, a second dose of 10 mg zavegeptan IN will be administered 24 hours after the first dose. Participants will be instructed to eat a butterscotch candy approximately 5 minutes prior to zavegeptan IN administration in period 2. Taste assessments will be compared for the 14 subjects after zavegeptan administration alone in period 1 vs. zavegeptan and butterscotch candy in period 2. Administering a second dose of 10 mg zavegeptan IN 24 hours after the first dose is well-supported by zavegeptan IN clinical trials data which shows no dose-limiting AEs after administering single doses as high as 40 mg IN and multiple doses of 20 mg for up to 14 days (refer to IB).

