2.2.2.3. Clinical Pharmacology

Based on the completed clinical studies of IN and PO zavegeptan, the following observations were made regarding the zavegeptan PK properties. Zavegeptan is rapidly absorbed (T_{max} : 0.54 hours) following a single zavegeptan 10 mg IN dose. The terminal elimination half-life of zavegeptan 10 mg IN dose is approximately 3 hours.³⁵ While the effective half-life of zavegeptan, which is considered more clinically relevant than the elimination half-life as it takes into account the entire plasma concentration-time profile, ranged from approximately 5 to 8 hours across dose levels ranging from 5 to 40 mg IN. Zavegeptan exhibits less than dose-proportional increases in exposure following single IN dose administration over the dose range from 1 mg to 40 mg. No evidence of meaningful accumulation was observed across a dose range of 5 to 20 mg zavegeptan IN after repeated QD dosing.

The results of the DDI study showed that co-administration of sumatriptan with zavegeptan IN does not result in a meaningful change in the PK of sumatriptan or of zavegeptan.

Co-administration of sumatriptan with zavegeptan IN does not cause elevations in mean arterial blood pressure or of systolic or diastolic blood pressure greater than those observed with sumatriptan alone. Lack of a clinically significant effect on the exposures of EE and LNG following co-administration of zavegeptan 20 mg IN and oral contraceptive support that zavegeptan is not a clinically relevant inhibitor of CYP3A4. Zavegeptan may be administered with an oral contraceptive without dose frequency adjustment. A 16% increase in the C_{max} and a 1.9-fold increase in zavegeptan AUC were observed in participants with moderate hepatic impairment.

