6.1.2. Zavegepant PK Parameters

The PK parameters of zavegepant will be listed and summarized descriptively for each collection method (Tasso-Plus, Tasso-M20 and venous phlebotomy), and by race (non-Japanese and Japanese), as data permits for the PK Parameter Analysis Set. Each zavegepant PK parameter will be summarized including the set of summary statistics as specified in Table 3.

For AUC_{last} , AUC_{inf} , and C_{max} , box and whisker plots for individual participant parameters will be constructed for each collection method and overlaid with geometric means.

Table 3. PK Parameters to be Summarized Descriptively by Collection Method and Race

Parameter	Summary Statistics
AUC_{inf} , AUC_{last} , C_{max} , CL/F , V_z/F	N, arithmetic mean, median, SD, %CV, minimum, maximum, geometric mean and geometric %CV
T_{max} , T_{last}	N, median, minimum, maximum
$t_{1/2}$	N, arithmetic mean, median, SD, %CV, minimum, maximum

Supporting data from the estimation of $t_{1/2}$ and AUC_{inf} will be listed by collection method and by race: terminal phase rate constant (k_{el}); goodness of fit statistic from the log-linear regression (r^2); the percent of AUC_{inf} based on extrapolation ($AUC_{extrap}\%$); and the first, last, and number of time points used in the estimation of k_{el} . This data may be included in the clinical study report.

For the Tasso vs. Venous comparison, natural log-transformed zavegepant AUC_{inf} (if data permit), AUC_{last} and C_{max} will be analyzed using a mixed effect model with blood collection method as fixed effect and participant as random effect. Estimates of the adjusted mean differences (Test – Reference) and corresponding 90% CIs will be obtained from the model with Venous as the Reference group and Tasso-M20 (or Tasso-Plus) as the Test group. The adjusted mean differences and 90% CIs for the differences will be exponentiated to estimate the adjusted geometric means ratio (Test/Reference) and 90% CIs for the ratios.

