For race comparison, natural log-transformed zavegepant AUC_{inf} (if data permit), AUC_{last} and C_{max} will be analyzed using an ANOVA model with race as fixed effect. Estimates of the adjusted mean differences (Test – Reference) and corresponding 90% CIs will be obtained from the model with non-Japanese as the Reference group and Japanese as the Test group. The adjusted mean differences and 90% CIs for the differences will be exponentiated to estimate the adjusted geometric means ratio (Test/Reference) and 90% CIs for the ratios.

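### Japanese venous profiles run to 24 h and all other profiles to 12 h, so the race and Tasso–venous contrasts of k_el-based parameters are mixed with sampling schedule

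*Protocol*

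**What the plan says.** **Schedules (Protocol 4.1 and Table 2).**
- Tasso samples, in all participants: 0.5, 1, 2, 4, 8 and 12 h.
- Venous samples, non-Japanese participants: the same six times.
- Venous samples, Japanese participants: these six plus 0, 0.25, 1.5, 3, 6 and 24 h. That is 12 samples, 11 of them post-dose.

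**Reasons given (Protocol 4.2).** The 12 h window is justified for comparing concentrations over time between the two methods. The 24 h window is justified for half-life: "having PK timepoints up to 24 hours will cover >3 half-lives, which will be sufficient to adequately estimate zavegeptant half-life in Japanese". The same paragraph gives two half-lives, "elimination half-life of ~ 3 hours and an effective half-life of 6.55 hours", and does not say which one the count of three refers to. Protocol 2.2.2.3 adds: "The terminal elimination half-life of zavegeptan 10 mg IN dose is approximately 3 hours". It says the effective half-life "ranged from approximately 5 to 8 hours across dose levels ranging from 5 to 40 mg IN".

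**Parameters.** t1/2, CL/F and Vz/F are primary PK parameters for all participants, as is AUCinf in Protocol Section 3. Protocol Table 3 and SAP Table 2 define t1/2 as the terminal half-life from k_el. AUCinf, t1/2, CL/F and Vz/F carry a footnote making them conditional on the data permitting.

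**Analysis (SAP 6.1.2).** The PK parameters "will be listed and summarized descriptively for each collection method (Tasso-Plus, Tasso-M20 and venous phlebotomy), and by race". AUCinf (if data permit), AUClast and Cmax are compared between methods in a mixed model. For race, the same three "will be analyzed using an ANOVA model with race as fixed effect". Both comparisons give adjusted geometric mean ratios with 90% CIs. The SAP lists k_el, r², the extrapolated percentage of AUCinf, and the first, last and number of points used for k_el. It sets no limit on any of them and does not ask for common sampling times.

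**The concern.** k_el is fitted to the end of the profile. With the last three points, for example, it comes from 8, 12 and 24 h in a Japanese venous profile and from 4, 8 and 12 h in every other profile. If decline slows over time, the later window gives a smaller k_el in the same person. That means a longer t1/2 and a larger AUCinf. The denser early sampling also changes the area before the tail.

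Two contrasts are exposed:
- **Race.** Japanese venous values come from one schedule and non-Japanese venous values from another. Race and schedule cannot be separated.
- **Tasso versus venous within Japanese participants.** The two profiles of one person end at different times.

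In non-Japanese participants the Tasso and venous times are identical, so their method contrast is unaffected.

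What is at stake is interpretation. Protocol 4.2 says the Japanese data are meant to support development in Japan, and the Tasso–venous ratio is the bridging result for paediatric use. A few per cent in AUCinf, or a larger shift in t1/2, could be read as a property of the population or the device when it comes from the clock.

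**Working it through.** **1. The plan's own figure.** Coverage = last sampling time ÷ half-life.

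| Last sample | Terminal, 3 h | Effective, 6.55 h |
|---|---|---|
| 24 h | 24/3 = 8.0 | 24/6.55 = 3.66 |
| 12 h | 12/3 = 4.0 | 12/6.55 = 1.83 |

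The statement that 24 h covers more than three half-lives is reproduced on either basis. At 12 h it is met with the terminal half-life and not with the effective one.

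**2. Share of AUC beyond the last sample.** Mono-exponential decline is assumed: share = exp(−ln 2 × T / t1/2).
- T = 12 h: 6.25% (3 h) or 28.1% (6.55 h).
- T = 24 h: 0.4% (3 h) or 7.9% (6.55 h).

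**3. Effect of schedule alone.** Noise-free profiles with no true difference were put through non-compartmental analysis on each schedule. Assumptions, none of them in the documents: linear-up/log-down trapezoids, zero at time 0, k_el from the last three points, and a quantifiable 24 h value (no LLQ is given). Each ratio is 24 h schedule ÷ 12 h schedule.

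*Mono-exponential*, absorption set to give the protocol's T_max of 0.54 h:
- 3 h: t1/2 3.00 and 3.00 h, ratio 1.00; AUCinf 4.292/4.210 = 1.02.
- 6.55 h: t1/2 6.55 and 6.55 h, ratio 1.00; AUCinf 9.408/9.312 = 1.01.

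*Two-phase, slow phase 3 h* (fast phase 0.5–1.2 h): t1/2 ratio about 1.0–1.4, AUCinf ratio about 1.03–1.04.

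*Two-phase, slow phase 6.55–8 h, fast phase 1.2–2 h* (t1/2 ratio about 1.5–1.8, AUCinf ratio about 1.06–1.12). Three of the cases, with an assumed absorption rate of 5–8 per hour:

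| Fast share / fast t1/2 / slow t1/2 | t1/2, 12 h schedule | t1/2, 24 h schedule | Ratio |
|---|---|---|---|
| 0.8 / 1.2 h / 6.55 h | 4.2 h | 6.3 h | 1.5 |
| 0.9 / 1.5 h / 6.55 h | 3.0 h | 5.4 h | 1.8 |
| 0.8 / 1.5 h / 8 h | 4.3 h | 7.2 h | 1.7 |

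*Two-phase, first phase 3 h and slow phase 6.55 h* (slow share 10% or 30%): t1/2 4.01/3.43 = 1.17 or 5.07/4.22 = 1.20; AUCinf 4.801/4.632 = 1.04 or 5.810/5.537 = 1.05. The 1.5–1.8 range therefore needs a short fast phase as well as a long slow one.

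**4. Source of the AUCinf shift.** In the three tabulated cases, removing only the 24 h sample still leaves a ratio of about 1.03–1.04, because the extra samples between 0.25 and 6 h remain. Dropping the 24 h point is not enough; the whole time grid has to match.

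**5. Dilution in the Tasso–venous ratio.** Suppose the model is fitted to the seven complete pairs of one device. A within-person venous/Tasso AUCinf ratio of 1.12 in j Japanese participants then moves the Tasso/venous geometric mean ratio to 1.12^(−j/7). That is 0.94 for j = 4 and 0.97 for j = 2. The race ratio is not diluted.

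**6. Precision.** One-compartment profiles with an assumed 20% residual error give these 5th–95th percentiles for estimated t1/2:
- True 3 h: 2.4–4.0 h (12 h schedule) and 2.7–3.4 h (24 h schedule).
- True 6.55 h: 4.2–14.1 h (12 h schedule) and 5.2–8.8 h (24 h schedule).

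**The case against.** The case for leaving the plan alone has real force.

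- **The larger ratios need an assumed slow phase.** The protocol puts the terminal half-life at about 3 h. Ratios of 1.5–1.8 arise only if the terminal phase is really 6.55–8 h, which treats an effective half-life as a terminal one. This stands. The documents do not establish that decline is two-phase. A twofold gap between the stated terminal and effective half-lives only makes it unsafe to presume a single phase.
- **The scope is small.** The mismatch needs optional participants, at most 4. There is no hypothesis or decision rule (Protocol 9.1, SAP 5.1), and the paired concentration comparison is untouched. Of the four parameters only AUCinf is modelled; t1/2, CL/F and Vz/F are descriptive. All this stands and limits the weight of the point.
- **The parameters are conditional, and the k_el points are listed.** This does not help much. No criterion defines when data permit. SAP 5.3.1 codes a parameter as not calculated only when it cannot be derived, and stops an analysis only when more than 50% are so coded. Three declining points to 12 h will give a k_el. A listing lets a reader see different windows but does not make the ratio comparable.

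A reader might go further and infer that, by the protocol's own standard, 12 h sampling cannot measure half-life or the parameters built on it. The documents do not support that. The endpoint is the terminal half-life, and 12 h is 4 of those at about 3 h. Only the effective half-life puts 12 h below three, and Section 4.2 does not say which is meant.

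**Conclusion.** The point holds as a comparability defect. If Japanese participants enrol, the race contrast and the Japanese part of the Tasso–venous contrast compare k_el-based parameters from different schedules, and nothing in the SAP prevents this. The direction is known where decline slows: Japanese venous t1/2 and AUCinf are pushed up.

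The size is not known. On the stated assumptions it runs from nothing in t1/2 and 1–2% in AUCinf (single phase), through about 1.0–1.4 and 1.03–1.04 (3 h slow phase), to about 1.5–1.8 and 1.06–1.12 (6.55–8 h slow phase after a short fast phase). If the 24 h value is not quantifiable, the tail part disappears and the early-sample part remains.

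Section 4.2 is also unclear. With 6.55 h, the 12 h window falls short of the standard used for the 24 h one. With 3 h, 12 h already meets it, and the stated reason for the 24 h sample weakens. This should be clarified, but rewording that section changes no result. The point is worth acting on because the remedy is cheap, not because a large bias has been shown.

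**What to change.** In SAP 3.1.2 and 6.1.2, state that for the Tasso–venous and race comparisons k_el, t1/2, AUCinf, CL/F and Vz/F are derived from the six shared times (0.5, 1, 2, 4, 8 and 12 h) in every profile. Report the Japanese venous values from the full schedule to 24 h in a separate descriptive table, labelled as such. The 24 h sample then keeps its stated purpose without entering the contrasts.

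A cap on the extrapolated share of AUCinf, such as 20%, is not a substitute. In the 6.55–8 h slow-phase cases with a short fast phase, extrapolation at 12 h is only 4–13%, so they would all pass. The cap would act on the single-phase 6.55 h case (about 29% in the non-compartmental run), where t1/2 is not biased.

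The cost is SAP text and a second non-compartmental run for at most 4 participants, with no new samples. The downside is a less precise Japanese k_el in the comparison, as step 6 of the working shows.

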4.2.1. Choice of Contraception/Barrier Requirements

Human reproductive safety data is not available for zavegeptan, but no evidence of embryo lethality and teratogenicity was found in animal embryofetal development studies in rats and rabbits with zavegeptan (refer to IB). Therefore, the use of a highly effective method of contraception is required (see [Appendix 4](#)). No data are available on the potential in vivo transfer of zavegeptan or its metabolites into human breast milk; therefore, lactating women must not receive zavegeptan. Only male and non-pregnant/non-lactating female participants will be included in the study.

4.3. Justification for Dose

The 10 mg IN dose of zavegeptan was selected as the optimal therapeutic dose for the acute treatment of migraine as it provided efficacy with minimized systemic exposure of zavegeptan. Based on that, this dose was the approved dose by the FDA for the acute treatment of migraine. Therefore, the exposure achieved following 10 mg zavegeptan IN is the most relevant for this study and for future pediatric studies. Overall, the data demonstrated that IN zavegeptan 10 mg is effective for the acute treatment of migraine.

4.4. End of Study Definition

The end of the study is defined as the date of the last visit of the last scheduled procedure shown in the [SoA](#) for the last participant in the trial.

A participant is considered to have completed the study if they have completed all periods of the study, including the last visit.

5. STUDY POPULATION

This study can fulfill its objectives only if appropriate participants are enrolled, including participants across diverse and representative racial and ethnic backgrounds. If a prescreening tool is utilized for study recruitment purposes, it will include collection of information that reflects the enrollment of a diverse participant population, including, where permitted under local regulations, age, sex, race, and ethnicity. The following eligibility

PFIZER CONFIDENTIAL

CT02-GSOP Clinical Pharmacology Protocol Template (14 April 2023)

Page 34

criteria are designed to select participants for whom participation in the study is considered appropriate. All relevant medical and nonmedical conditions should be taken into consideration when deciding whether a particular participant is suitable for this protocol.

Prospective approval of protocol deviations to recruitment and enrollment criteria, also known as protocol waivers or exemptions, is not permitted.

5.1. Inclusion Criteria

Participants are eligible to be included in the study only if all of the following criteria apply:

Age and Sex:

1. Male or female ≥ 18 years of age and older at the time of signing the ICD.
 - Refer to [Appendix 4](#) for reproductive criteria for male ([Section 10.4.1](#)) and female ([Section 10.4.2](#)) participants.
 - For Japanese participants to be enrolled, they need to meet the following inclusion criteria: Japanese participants must have 4 Japanese grandparents who were born in Japan.

Other Inclusion Criteria:

2. Male and female participants who are overtly healthy as defined by:
 - the absence of clinically significant illness and surgery within 4 weeks prior to dosing. Participants vomiting within 24 hours Predose will be carefully evaluated for upcoming illness/disease.
 - the absence of clinically significant history of neurological, endocrinial, cardiovascular, pulmonary, hematological (eg, neutropenia), immunologic, psychiatric, gastrointestinal, renal, hepatic, and metabolic disease.
3. BMI 16.0-32.0 kg/m² and body weight ≥ 45.0 kg (99 lb).
4. Females must not be breastfeeding or lactating and must have a negative urine or serum pregnancy test (minimum sensitivity 25 IU/L or equivalent units of HCG) at screening. WOCBP must have negative urine or serum pregnancy test at admission.
5. Participants are willing to consume a butterscotch candy.

